To assess the effectiveness of this multilevel intervention, called the workplace *Metabolic Health Improvement Program (MHIP)*, we will conduct a double-randomized trial in partnership with the clinical trials division of a large Northern California-based academic healthcare system, Sutter Health ($N=700$ employees on $N=16$ hospital campuses). We will first cluster-randomize 8 Sutter Health hospital campuses to the SSB sales ban condition and 8 campuses to serve as controls (no sales ban). Across these 16 campuses, we will further randomize heavy-SSB-consuming employees (>30 oz/week) to receive a brief SSB counseling intervention delivered remotely or to a control condition.^{11,12} The **primary outcomes** are central obesity (e.g., waist circumference) and change in serum insulin sensitivity (homeostatic model assessment [HOMA] ratio). **Secondary outcomes** include changes in SSB consumption, Body Mass Index (BMI), and lab values to include: lipid profile, triglycerides, triglyceride:HDL ratio, uric acid, ApoA, ApoB, lactate, ALT/AST, GGT, fasting glucose, fasting insulin, HbA1c. We will assess dietary composition remotely using the Automated Self-Administered 24-hour (ASA-24) at baseline, 6 and 12 months, and waist circumference remotely with empirically validated instructions and a standardized tape measure provided to participants. We will collect blood samples in the workplace labs at baseline and 12 months. All analyses will consider compensatory changes in at-home SSB intake, calories from sugar, and total calories. Aims are:

Aim 1: How well does each intervention work alone? We will assess the independent effects of the brief counseling intervention and workplace SSB sales ban on changes in primary and secondary outcomes. We will compare outcomes across employees exposed to the brief intervention only ($n=175$), SSB sales ban only ($n=175$), and no intervention ($n=175$). *We hypothesize that the brief counseling intervention and sales ban will each independently decrease waist circumference and HOMA relative to no intervention. Those at high risk (baseline BMI >25 , ethnic-minority, and lower-occupational status) will benefit more from the interventions.*

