Waist Circumference	A tape measure with instructions will be provided to the participant to measure at the designated timepoints.	X	X	X
Fasting Blood Draw	The collection will include: complete metabolic and lipid panel, uric acid, ApoB, GGT, glucose, insulin, HbA1c. These are biomarkers that are risk factors for poor metabolic health, diabetes, and cardiovascular disease	X		X
BevQ	This questionnaire seeks to quantify the frequency, type and volume of beverages consumed at work and home.	X	X	X

**SUTTER HEALTH
INSTITUTIONAL REVIEW BOARD**

Protocol Summary Form

ASA 24	This is a web-based, 24-hour dietary recall tool developed by the National Cancer Institute	X	X	X
Stanford Leisure Time Scale (L-CAT)	This is a scale that measures physical activity.	X	X	X
*PROMIS4a Depression	Assesses the presence and severity of symptoms of depression.	X	X	X
Beverage Craving Questionnaire (FCQ-T-R)	Assesses the following: 1) preoccupation with sweetened beverages; 2) loss of control; 3) positive outcome expectancy; 4) emotional cravings	X		
Reward Based Eating Drive (RED-13)	Assesses three aspects of drive to eat: 1) loss of control; 2) lack of satiety; 3) preoccupation with food	X	X	X
Perceived Stress Scale	This is a widely used questionnaire to assess stress levels. It evaluates the degree to which an individual has perceived life as unpredictable, uncontrollable, and overloading over the previous month.	X	X	X
Copenhagen Burnout Inventory (CBI)	This six-item inventory measures personal burnout experienced by participants.	x	x	x
Self-Efficacy	These questions are used to determine if an individual exhibits intention to reduce SSB consumption.	X	X	X
Science of Behavior Change Texts Parent Grant	Assesses craving, psychological stress, consumption and self-efficacy (two texts/day x four days/week)	X	X	X
Science of Behavior Change Texts Supplemental Grant	Assesses craving, psychological stress, consumption and self-efficacy (two texts/day x four days/week)	Additional texts will be sent at the following time periods: 1, 2, and 3 months after SSB intervention.		
EPIC EMR	Lab results from the blood draw will be extracted from EPIC utilizing the resources of the Center for Health Services Research (CHSR). Limited data from the medical record will be extracted by CHSR that looks at metabolic health.	X		X
Incentive Gift		X	X	X

**SUTTER HEALTH
INSTITUTIONAL REVIEW BOARD**

Protocol Summary Form

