***Patient-Reported Outcomes Measurement Information System (PROMIS):** We have selected a self-report measures of depression which are person-centered which all study participants will be asked to complete. We will investigate the possible correlation between SSB consumption, general health and depression as well as change over time between the intervention and control campuses. Subjects who report high levels of depression will be provided with contact information to Sutter Health's Employee Assistance Program (EAP). No documentation will be placed in the subject's medical or employment record.

REDCap will be set-up with a notification alerting the CRCs when the depression scores result with severe depression. When the participant completes their questionnaires, the Clinical Research Coordinators will review the depression questionnaire. If a participant scores a severe depression (score, a phone call will be made to the participant using a script. A form has been created and will be used as documentation. This includes a script for leaving a message and for a live call. During a live call only, the Clinical Research Coordinator will inform the participant of their high score and will with the phone number to Sutter Health's EAP.

Demographics: Including gender, ethnicity, primary work location, occupational status, income, and usual number of worked shifts each week will be recorded via REDCap.

Medical History: Concurrent medications and general medical history will be obtained directly from study participants with an emphasis on metabolic history such as diabetes. Data will be recorded via REDCap

Height, weight, and waist circumference measurements: Subjects will be asked to record their self-reported height in REDCap. Height and weight will be measured using a standard scale with an attached stadiometer in a semi-private location at the affiliate and record their weight and height in REDCap. A tape measure and instructions on measuring waist will be sent to the participant's home. They will record the measurement in REDCap.

Fasting Blood Draw: A fasting blood draw will take place at the draw station of the local affiliate. Labs will be drawn at baseline and at 12-months. The panels will be comprised of metabolic and lipid panels that pertain to metabolic syndrome. Labs will be accessible to participants using My Health Online.

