Analytic Plan: We will analyze Aim 1 using all data collected at the baseline, 6- and 12-month time points. First, we will use ANOVA to compare group means and determine whether there is a significant main effect for each intervention (the sales ban and the brief intervention). Based on theory and our previous studies, we know that baseline risk factors and demographics are likely relevant to the impact of these interventions; those at greater baseline risk tend to benefit more from the interventions. Therefore, each dependent variable will also be examined using a linear regression model, which allows us to observe the main effects of these factors. For example, the model predicting HOMA change would include assignment to the sales ban condition (coded as 0/1), assignment to the brief intervention condition (coded as 0/1), baseline HOMA, baseline SSB consumption, baseline BMI, race/ethnicity, and sex. Subsequent models can consider baseline BMI > 25, ethnicity and job classification. The procedure for analyzing each outcome would be the same, but with each primary and secondary outcome substituted for HOMA in turn.

For SSB consumption, we will examine at-work consumption, at-home consumption, and total consumption as separate outcomes to thoroughly investigate the impact of the interventions across work and home environments. We will similarly check for potential compensatory consumption in sugar from calories and total calories for participants in the intervention conditions relative to controls. If ASA-24-based total calories or calories from sugar disproportionately increase in the intervention groups, this suggests a compensatory effect.

Although we believe our strategy of cluster randomization and controlling for individual differences that can vary regionally (such as ethnic distribution) is sufficient, we will also analyze the effects of the brief intervention via an exploratory mixed regression model, with individuals nested within sites, to see if study site was an important factor. If it is, we will consider mixed models where possible.

**SUTTER HEALTH
INSTITUTIONAL REVIEW BOARD**

Protocol Summary Form

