Power Calculations: Power calculations are based on changes observed in the pilot study and response rates from the current Sutter Health trial. Calculations are conservative, based on 80% retention of participants after 12 months. With an initial N of 700 drawn from 16 Sutter Health sites randomly assigned to the sales ban and control conditions, and with participants within those sites randomly assigned to brief intervention/no brief intervention conditions, 80% retention would result in an overall N of 550 at 12 months. This results in approximately 138 in each of four experimental conditions: brief intervention + sales ban, the brief intervention only, sales ban only, and no intervention. Power analysis for a full factorial design conducted with the BDEsize¹⁰⁹ package within R¹¹⁰ indicates that with 80% power and an alpha level of .05, we will be able to detect effect sizes as small as .08 for the effect of each intervention on each outcome.

Anticipated Problems and Alternative Approaches: One potential problem is attrition, particularly biased attrition. We have calculated the sample to allow for up to 20% attrition; this is a conservative number based on our current Sutter Health data. In the UCSF pilot, which took place entirely pre-pandemic, we achieved a 94.4% response rate for blood draws. The existing study team has experience with the challenges of retaining a sample of health care workers during a challenging time and can use the same techniques (e.g., email and phone outreach) to reduce attrition here. We will conduct statistical tests to determine if attrition is biased on baseline risk levels, demographic factors (including regional differences), or study condition.

As with all self-report data, the survey data on SSB consumption could be biased, perhaps particularly for intervention participants who want to self-present improvement. However, the anthropometric and blood measures are objective and should show a consistent pattern with the SSB changes. Standard data cleaning procedures should reveal any extreme cases of self-representation bias. For SSB consumption data, we have also established a convention in previous studies of pruning outliers that are more than 4 SD away from the mean to reduce error from participants who may have responded inaccurately.

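### Waist circumference, a primary outcome, is self-measured at home with no stated number of readings, averaging rule or disagreement rule; averaging two or three readings would cheaply cut random error.

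*Combined protocol and SAP*

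**What the plan says.** Section 1 (Study Aim/Purpose) states that the primary outcomes "are central obesity (e.g., waist circumference) and change in serum insulin sensitivity". The same section plans to assess "waist circumference remotely with empirically validated instructions and a standardized tape measure provided to participants".

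The schedule table in section (4b) Procedures lists waist at baseline, 6 and 12 months: "A tape measure with instructions will be provided to the participant to measure at the designated timepoints". The paragraph on height, weight and waist in (4b) says that the tape and instructions go to the participant's home, and then: "They will record the measurement in REDCap".

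No section gives a number of readings, an average, or a rule for readings that disagree. The only numeric outlier rule, in the Aim 1 text on anticipated problems in (4c), covers beverage intake: "For SSB consumption data, we have also established a convention in previous studies of pruning outliers".

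For the analysis, the Aim 1 analytic plan says "We will analyze Aim 1 using all data collected at the baseline, 6- and 12-month time points". It gives a regression for HOMA change that includes the baseline value, and adds: "The procedure for analyzing each outcome would be the same, but with each primary and secondary outcome substituted for HOMA in turn". Waist change therefore goes through the same model.

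**The concern.** A tape reading taken by an untrained person at home carries random error from tape height, tension, posture and breathing. A change score takes that error in twice, once at baseline and once at follow-up. If each visit yields one reading, nothing in the stated procedure dilutes it.

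The cost would be power and interval width for a primary outcome. Repeating the reading at the same sitting needs no visit, staff or new equipment. The choice cannot be made later: replicates not taken at baseline cannot be reconstructed, and every change score depends on baseline.

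**Working it through.** **The plan's own figures.** The plan gives no figure for waist measurement error and no waist SD. Its power statement starts from "80% retention would result in an overall N of 550 at 12 months" (80% of 700 is 560; I use the stated 550). For a 2×2 factorial with N = 550, 1 df, two-sided alpha .05, 80% power and no clustering, the smallest detectable effect is Cohen's f = 0.120 (d = 0.239). This matches the .12 given for the interaction. The .08 given for main effects is not reproduced: read as f, it has 46.5% power. The plan does not name the effect-size metric, so this does not prove .08 wrong. Neither figure depends on the number of waist readings, and neither converts to centimetres without an SD.

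**Inputs.** From the documents: 550 at 12 months, so about 275 v 275 for each main effect; 16 campuses, so 550/16 = 34.4 per campus. Assumed: SD of true 12-month change s = 4 to 6 cm; independent error SD of one reading e = 1 to 3 cm.

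**Formulas.** With k readings averaged at each timepoint:

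- Var(change) = s² + 2e²/k
- Equivalent sample-size ratio = Var(k = 1) / Var(k)
- Detectable difference = (1.960 + 0.842) × SD × √(2/275) = 0.2389 × SD

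**Individual-level comparison.**

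| s, e (cm) | Var, k = 1 | Var, k = 2 | Var, k = 3 | Equivalent extra N, k = 2 | Equivalent extra N, k = 3 |
|---|---|---|---|---|---|
| 6, 1 | 38.0 | 37.0 | 36.7 | 3% | 4% |
| 5, 2 | 33.0 | 29.0 | 27.7 | 14% | 19% |
| 4, 3 | 34.0 | 25.0 | 22.0 | 36% | 55% |

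In the middle row, the SD of change is 5.74, 5.39 and 5.26 cm for one, two and three readings. The detectable difference is 1.37, 1.29 and 1.26 cm. Power for an assumed 1 cm effect is 53%, 59% and 61%.

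**Error partly shared between readings.** If half of the error variance is common to all readings in a sitting, three readings leave e²(½ + ½/3) = ⅔e². The variances become 37.3, 30.3 and 28.0, so the equivalent extra N falls to 38/37.3 = 2%, 33/30.3 = 9% and 34/28 = 21%.

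**Adjustment for baseline.** If true change is unrelated to the baseline level and true waist varies between people with SD B, adjustment removes e⁴/(B² + e²) from the variance. Take B = 10 cm (assumed) and the bottom row. One reading gives 34 − 81/109 = 33.26. Three readings have error variance 9/3 = 3, which gives 22 − 9/103 = 21.91. The cut is 34%, against 35% unadjusted, so adjustment does not remove the problem.

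**Sales-ban effect.** The variance of a campus mean is ICC × V + (1 − ICC) × V/34.4, and averaging lowers only the second term. In the middle row V = 33, and three readings remove (33 − 27.67)/34.4 = 0.155.

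- ICC 0.01 (assumed): 0.33 + 0.950 = 1.280; cut 0.155/1.280 = 12%
- ICC 0.05 (assumed): 1.65 + 0.912 = 2.562; cut 0.155/2.562 = 6%
- Individual-level comparison: 5.33/33 = 16%

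**The case against.** The strongest objection is that a singular noun in a short procedures paragraph does not fix a design. The recorded measurement could already be an average, and the instructions described as validated may ask for repeats. This stands. A reader might infer that the protocol prescribes one reading per visit; the documents do not support that, because they are silent on the number. What remains is that the definition of a primary outcome is open, and that the text describes one entered value with no combining rule.

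A reader might also infer that a mistyped waist would stay in the data. That does not follow. The same Aim 1 text mentions standard data cleaning, although it frames this around self-presentation and sets no waist rule. Entering inches as centimetres is, moreover, a units problem: three readings entered in the wrong unit average to the same error. It argues for an entry check, not for replicates.

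The gain may also be modest. With a reading-error SD near 1 cm it is a few percent. For a 2.1 cm difference, the size of the pilot's change, power is already about 99% with one reading at SD 5.74 cm, ignoring clustering. That 2.1 cm is an uncontrolled before-after change, however, so a smaller between-group difference is plausible, and there the gain counts for more.

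**Conclusion.** The point holds as a cheap improvement in precision for an incompletely defined primary outcome. If one reading is taken, averaging three would be worth about 4% to 55% more participants for individual-level comparisons. That range assumes a true-change SD of 4 to 6 cm and independent reading error of 1 to 3 cm; none of these values is in the documents. With half of the error variance shared between readings, the range is about 2% to 21%.

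A reader might infer that both interventions gain equally. They do not: the sales ban is randomized by campus, and averaging leaves between-campus variance untouched. Nor would averaging make a self-measured waist objective. It removes only independent error within a sitting, and leaves day-to-day variation, consistent technique error and bias from unblinded self-measurement as they were.

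If the instruction sheet already asks for repeats, the precision gain may already be in hand. The protocol would then need only to state the number of readings, how they are combined and how disagreement is handled.

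**What to change.** In the (4b) waist paragraph, the schedule table and the instruction sheet, specify the following for baseline, 6 and 12 months, identically in all arms:

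- At least two, preferably three, readings at one sitting, with the tape removed and re-placed each time.
- A separate REDCap field for each reading, with fixed units.
- The analysed outcome defined as the mean of the readings.
- An automatic prompt to re-measure when readings differ by more than an amount set in advance.
- A separate units and range check at entry, to catch gross slips that averaging cannot correct.

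State in (4c) that waist change is computed from the averaged values. The cost is one or two extra fields per timepoint, the prompt and check, a line of instructions, and one to two extra minutes per participant per visit. No staff, visits or equipment are added. The change has to be in place before baseline measurement to have its full effect.
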